4.3.1 Exploratory endpoints

Clinical status based on a 7-point ordinal scale.

The scale consists of the the following categories:

- 1. Death
- 2. Hospitalized, requiring invasive mechanical ventilation or extracorporeal membrane oxygenation (ECMO)
- 3. Hospitalized, requiring non-invasive ventilation or high flow oxygen devices
- 4. Hospitalized, requiring supplemental oxygen
- 5. Hospitalized, not requiring supplemental oxygen requiring ongoing medical care
- 6. Hospitalized, not requiring supplemental oxygen no longer requires ongoing medical care
- 7. Not hospitalized

PK parameters will be calculated for emapalumab and anakinra by non-compartmental analysis and population analysis, as applicable.

PD biomarkers: Change from baseline in CXCL9, IFN γ , IL-1, IL-6, sIL-2R and selected biomarkers relevant for hyperinflammation.

5 Investigational plan

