5.5 Efficacy and safety assessments

5.5.1 Study schedule

5.5.1.1 Schedule of events

Version 7.0 Final Protocol, Date 24 Jun 2020

Table 2 Schedule of Events

Emapalumab/Anakinra

	SCREENING	TREATMEN	T PERIOD		Early FU	FOLLOW-UP PERIOD				
ASSESSMENT	Up to 72h	Visit 1	Visit 2	Visit 3	Visit 4	Visit 5	Visit 6	Visit 7	Visit 8/TC	Visit 9/TC
	prior to Visit 1	Day 1 (Baseline)	Day 4	Day 7	Day 10	Day 13	Day 15 (± 1 day)	Day 28 (± 3 days)	Week 6 (± 5 days)	Week 10 (± 5 days)
Informed consent	х									
Eligibility criteria	Х	X1								
TB screening ¹³	х									
PCR SARS-CoV-2 ¹⁴	Х									
Patient information ²	х									
Symptom onset information	Х									
Physical examination ³	х									
Vital signs assessment ⁴	Х	Х	Х	Х	Х	Х	Х	Х		
ECG assessment	Х						Х	Х		
HRCT scan or X-ray of chest	X ⁵						Х	Х		
Laboratory assessments (local) ⁶	X ⁵	х	Х	Х	Х	Х	х	Х		
Urine pregnancy test ⁷	х						Х			
Randomization		х								
IMP administration ⁸		X					X			
Concomitant medication incl background therapy ⁹		x	х	х	х	х	х	x		
Pulmonary function ¹⁰		х	Х	Х	Х	Х	х	Х		
PaO ₂ /FiO ₂	Х						Х	Х		
Resting SpO ₂ (3 times per day)		Х	Х	Х	Х	Х	Х	X ¹⁸		
Hemogasanalysis		Х	Х	Х	Х	Х	Х	Х		
Oxygen supplementation		х	Х	Х	Х	Х	Х	Х		
MEWS score		х					Х	Х		
Clinical status 7 point ordinal scale		х	х	х	х	х	х	Х	х	Х

Confidential

Page 33 of 62

Clinical Study	No:	Sobi.IMMUNO-101
----------------	-----	-----------------

	SCREENING	TREATMEN	T PERIOD	Early FU	FOLLOW-UP PERIOD					
ASSESSMENT	Up to 72h prior to Visit 1	Visit 1	Visit 2	Visit 3	Visit 4	Visit 5	Visit 6	Visit 7	Visit 8/TC	Visit 9/TC
		Day 1 (Baseline)	Day 4	Day 7	Day 10	Day 13	Day 15 (± 1 day)	Day 28 (± 3 days)	Week 6 (± 5 days)	Week 10 (± 5 days)
Survival								х	Х	х
Time to hospital discharge								Х	Х	Х
Adverse events ¹¹		Х	Х	Х	Х	Х	Х	Х	Х	Х
Biomarkers ¹²		Х	Х	Х	Х	Х	Х	Х	Х	Х
PK: emapalumab/anakinra serum concentration ¹⁵		х	х	х	х	х	Х	х	х	х
Immunogenicity ¹⁶		х					Х	Х	Х	х
Viral shedding ¹⁷		х			Х		Х	Х	Х	Х

Abbreviations: CPAP, continuous positive airway pressure; ECMO, extracorporeal membrane oxygenation; FiO₂, fraction of inspired oxygen; HRCT, high resolution computed tomography; IMP, Investigational Medicinal Product; MEWS, modified early warning system; PaO₂, partial pressure of oxygen; SpO₂, peripheral capillary oxygen saturation During the treatment period (Days 1 to 15), clinical and laboratory assessments and procedures should preferably be performed before IMP administration. ¹Before study drug administration.

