²Includes demographics, medical and surgical history and prior medication.

³Including recording of body weight and length.

⁴Body temperature, blood pressure, heart rate, respiratory rate and oxygen saturation.

⁵HRCT scan results and laboratory results already available in medical records at the time of informed consent can be used to confirm eligibility, if collected within 72 hours. ⁶Ferritin, LDH, D-dimers. WBC with differential counts, RBC, Hb, Platelet count, Fibrinogen, Complement C3/C4, Prothrombin Time, Cardiac troponin, AST, ALT, total bilirubin levels, CRP and Creatinine.

⁷Only applicable for females of childbearing potential.

⁸Emapalumab will be administered once daily Days 1, 4, 7, 10 and 13 (Section 5.4.5.1). Anakinra will be administered 4 times daily for 15 days i.e., Day 1 to 15 (Section 5.4.5.2). ⁹For details, see Section 5.4.7.

¹⁰Requirement for invasive mechanical ventilation or ECMO.

¹¹Incidence, severity, causality and outcomes of treatment-emergent serious AEs, adverse events leading to premature discontinuation of study treatment and adverse events of special interest.

¹² PD biomarkers: CXCL9, IFNy, IL-1, IL-6, sIL-2R. Samples to be collected Visit 1:pre-dose and thereafter at Visits 2, 3, 4, 5 and 6: end of infusion. (for anakinra treated patients; samples will only be collected in connection with the first infusion per day) In addition, at Visits 8 and 9, a PD biomarker sample will be collected in case the patient is coming to the clinic for these visits.

¹³Local TB testing to confirm patient status. Test result are accepted post randomization not to delay treatment.

Confidential

Page 34 of 62

Version 7.0 Final Protocol, Date 24 Jun 2020

Sobi

Emapalumab/Anakinra

Emapalumab/Anakinra

¹⁴Local PCR testing to confirm patient SARS-CoV-2 diagnosis. For sites where PCR is not part of hospital routine for confirming diagnosis/eligibility, test results are accepted post randomization not to delay treatment.

¹⁵ PK blood samples will be collected at Visit 1: pre-dose and at end-of infusion (for anakinra after the first infusion per day), and thereafter at Visits 2, 3, 4, 5 and 6: at end-of infusion (for anakinra treated patients; samples will only be collected in connection with the first infusion). In addition, for emapalumab treated patients at Visits 7. For Visit, 8 and Visit 9, a PK sample will be collected in case the patient is coming to the clinic for these visits.

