5.5.5.2 Pharmacokinetics

PK blood samples will be collected for all patients receiving active study treatment. At Visit 1 sampling should be done pre-dose and at end-of infusion and during Visits 2, 3, 4, 5 and 6 a PK sample should be taken at end-of infusion. For anakinra treated patients; samples will only be collected in connection with the first infusion per day. In addition, for emapalumab treated patients, a PK sample will be collected also at Visit 7 (Day 28) and during follow-up on Visit 8 and 9 in case the patient is at the clinic for these visits. It should be noted that a separate iv line will have to be used when collecting the PK samples, ie not the same iv line as used for the iv infusion of active study treatment.

The date and time of blood sampling will be recorded in the CRF. Samples will be sent to a central laboratory for analysis.

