5.5.5.3 Pharmacodynamics

Blood samples for determination of CXCL9, IFN γ , IL-1, IL-6, sIL-2R and selected exploratory parameters will be collected at Visit 1 to 9 at the end of infusion (for anakinra treated patients; samples will only be collected in connection with the first infusion per day). The date and time of blood sampling will be recorded in the CRF. It should be noted that a separate iv line will have to be used when collecting the PD samples, ie not the same iv line as used for the iv infusion of active study treatment.

Samples will be sent to a central laboratory for analysis.

6 Quality control and quality assurance

This study will be conducted in compliance with this protocol, study specific procedures, CRO SOPs, Sobi SOPs, the ICH Guideline for GCP [1], and applicable regulatory requirements.

Version 7.0 Final Protocol, Date 24 Jun 2020

The Sponsor/CRO will establish a systematic, prioritized, risk-based approach to monitoring and, considering the current situation, will need to utilize remote monitoring. The Sponsor/CRO will develop a risk management plan with the aim to limit the contacts with patients and site personnel during the emergency period, while ensuring the patients safety and integrity, compliance with the protocol, study specific procedures and applicable regulatory requirements.

To ensure ongoing patient safety and well-being, and control risks to study critical processes, such as review of all informed consent forms and all primary efficacy variables, alternative mechanisms of oversight will be introduced (such as phone calls, video calls, remote monitoring etc). The Sponsor/CRO will also investigate if other measures for sharing data can be implemented, e.g. sharing de-identified source documents in shared drives/locations.

On-site monitoring visits will be postponed until the emergency period is over. Source documents will then be reviewed for verification of agreement with data in CRFs.

The investigator or institution guarantees access to source documents by Sobi, its representatives, and appropriate regulatory agencies.

The study site may be subject to a quality assurance audit by Sobi or its representatives, as well as inspection by appropriate regulatory agencies.

It is important that the investigator(s) and the(ir) relevant personnel are available during the monitoring visits and possible audits and that sufficient time is devoted to the process.

7 Statistical plan

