## 1 Abbreviations and definition of terms

AE	Adverse event
ALT	Alanine aminotransferase
ANCOVA	Analysis of covariance
AST	Aspartate aminotransferase
Baseline	Before study drug administration at Visit 1 (Day 1)
CRP	C-reactive protein
CSR	Clinical study report
CT	Computed tomography
CXCL9	Chemokine (C-X-C Motif) ligand 9
DRC	Data review committee
ECMO	Extracorporeal membrane oxygenation
ECG	Electrocardiogram
FDA	Food and Drug Administration
FiO 2	Fraction of inspired oxygen
Hb	Hemoglobin
ICH	International council of harmonization of technical requirements for registration of pharmaceuticals for human use
IL	Interleukin
i.v.	Intravenous
IMV	Invasive mechanical ventilation
LDH	Lactate dehydrogenase
MedDRA	Medical Dictionary for Regulatory Activities
MEW	The modified early warning score
PaO 2	Partial pressure of oxygen
pCO 2	Carbon dioxide tension
pO 2	Oxygen tension
PT	Preferred term
RBC	Red blood cells

SAE	Serious adverse event
SAP	Statistical Analysis Plan
SARS-Cov-2	Severe acute respiratory syndrome coronavirus 2
SD	Standard deviation
Sobi	Swedish Orphan Biovitrum
SOC	System organ class
SpO 2	Peripheral capillary oxygen saturation
SRC	Safety review committee
TEAE	Treatment emergent AE
WBC	White blood cells
WHO	World Health Organization

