**Table 2 Time windows**

Visit	Study Day	Study Day window
1	1 (Baseline)	≤1
2	4	2-5
3	7	6-8
4	10	9-11
5	13	12-14
6	15	15-16
7	28	Early follow-up
7/TC	Week 6	Only follow-up of survival and hospital discharge and continued AE reporting in accordance with the protocol.
8/TC	Week 10	

Unscheduled visit data will be considered when assigning assessments to the analysis visit. If more than one assessment of the variable (scheduled or unscheduled) falls in the same time window but on different days, the closest to the scheduled visit day will be taken, or the earlier, in the event the values are equidistant from the nominal visit date. If several measurements are collected during the selected day, the average (for numeric values)/worst (for categorical values) of the measurements will be taken.

In summaries of extreme values as opposed to visit-based summaries, all post baseline values collected are used including those collected at unscheduled visits regardless if the value is closest to the scheduled visit date or not. For summaries at a patient level, all values should be included, regardless of whether they appear in a corresponding visit-based summary, when deriving a patient level statistic such as a maximum.

Listings will display all values contributing to a time point for a patient.

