### **12.4.3 Pharmacodynamics**

Change from baseline in CXCL9, IL-1, IL-6, sIL-2R and any other selected biomarkers relevant for hyperinflammation that are collected, will be summarized with descriptive statistics by visit.

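### Protocol 5.5.5.3 and Table 2 footnote 12 disagree on whether the Visit 1 biomarker sample precedes the first infusion, and the SAP baseline window would not catch a post-infusion value

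*Protocol*

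**What the plan says.** Protocol 5.5.5.3 (Pharmacodynamics) states that blood for CXCL9, IFN-gamma, IL-1, IL-6, sIL-2R and selected exploratory parameters "will be collected at Visit 1 to 9 at the end of infusion". It makes no exception for Visit 1.

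Footnote 12 to Protocol Table 2 (Schedule of Events) covers the same samples: "Samples to be collected Visit 1:pre-dose and thereafter at Visits 2, 3, 4, 5 and 6: end of infusion". It adds Visits 8 and 9 only for patients who attend the clinic. It does not mention Visit 7, although the table marks a biomarker sample there.

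The SAP's list of definitions gives baseline as "Before study drug administration at Visit 1 (Day 1"), and Protocol 1.1 has the same definition. Protocol 4.3.1 sets the endpoint as "PD biomarkers: Change from baseline in CXCL9, IFN γ , IL-1, IL-6, sIL-2R and selected biomarkers relevant for hyperinflammation". SAP 12.4.3 summarises by visit "Change from baseline in CXCL9, IL-1, IL-6, sIL-2R and any other selected biomarkers relevant for hyperinflammation that are collected", so IFN-gamma is named in the protocol endpoint but not in the SAP analysis.

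For assigning values to visits, SAP 8.1 and SAP Table 2 put any value from Day 1 or earlier in the Visit 1 (baseline) window. Where several measurements fall on the selected day, "the average (for numeric values)/worst (for categorical values) of the measurements will be taken".

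**The concern.** The two protocol texts give incompatible times for one sample. A site that draws a single Visit 1 biomarker sample cannot comply with both. If it follows 5.5.5.3, the first sample in an active-arm patient comes after the first infusion, and by the documents' own definition that value is not a baseline. A pre-dose sample cannot be taken later, and the schedule has no biomarker sample at screening to fall back on.

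The problem falls unevenly across the arms. Standard-of-care patients receive no study infusion, so any Day 1 sample from them remains untreated. Comparing change from baseline between arms could then mean comparing changes from two different kinds of starting value. Protocol 3.1 describes the study as proof of concept intended to guide further development, and these cytokines are its mechanistic readout.

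**Working it through.** The documents give no figure to reproduce here. The check is a comparison of texts, a count, and a line of algebra.

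**Sampling time by visit.** Infusion days are from Protocol 5.4.5.1 and 5.4.5.2.

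| Visit | Protocol 5.5.5.3 | Protocol Table 2 with footnote 12 | Study infusion scheduled |
|---|---|---|---|
| 1 (Day 1) | end of infusion | pre-dose | emapalumab, anakinra |
| 2 to 5 (Days 4, 7, 10, 13) | end of infusion | end of infusion | emapalumab, anakinra |
| 6 (Day 15) | end of infusion | end of infusion | anakinra only |
| 7 (Day 28) | end of infusion | sample marked, time not stated | none |
| 8 and 9 (Weeks 6, 10) | end of infusion | only if the patient attends the clinic | none |

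Standard of care has no study infusion at any visit. The direct conflict is at Visit 1. Two further gaps appear. Both texts use end-of-infusion timing for emapalumab at Visit 6, two days after its last scheduled infusion on Day 13. Protocol 5.5.5.3 also uses it at Visits 7 to 9, when no arm is infused.

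**Does another passage settle Visit 1?** The general note to Protocol Table 2, repeated in 5.5.1.3, says that "clinical and laboratory assessments and procedures should preferably be performed before IMP administration". That is a preference, so it does not override a specific sampling instruction. The neighbouring PK section asks for two Visit 1 samples: "At Visit 1 sampling should be done pre-dose and at end-of infusion". The PD section has no such pre-dose clause.

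**How many patients.** With 18 patients per arm and two infused arms, 2 × 18 = 36 of 54 receive an infusion. If k patients in an active arm are sampled only after the infusion, k can be anything from 0 to 18. Across both arms the range is 0 to 36. The documents do not say which text sites follow.

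**What happens to the summary.** Let d be the average shift in a biomarker from just before to just after the first infusion (60 minutes for anakinra, 1 to 2 hours for emapalumab).

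- Baseline definition applied strictly: the k values are not baselines, and the number with a change from baseline in that arm falls from 18 to 18 − k.
- SAP window applied as written, one post-infusion sample: baseline becomes B + d, the patient's change is shifted by −d, and the arm mean by −(k/18) × d.
- SAP window applied as written, pre- and post-infusion samples both drawn: averaging gives (B + B + d)/2 = B + d/2, so the patient's change is shifted by −d/2.
- Standard of care: no study infusion, so no such shift.

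If the infusion lowers a marker (d negative), a later fall is understated; if it raises the marker, a later fall is overstated. The documents give no d for any marker, so neither sign nor size can be stated.

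**The case against.** The best defence is that 5.5.5.3 is a loosely compressed sentence and that sites would work from the schedule. Protocol 5.5.1.3 sends the reader to Table 2 for what is collected at Visit 1, and its footnote is the more detailed instruction. Both documents define baseline as before study drug, and the preference for assessing before dosing points the same way. Active-arm patients also have pre-dose PK and immunogenicity draws at Visit 1, so blood is taken at that point anyway. A mistimed sample could be detected, because the CRF records the date and time of each PD sample and the start and end of each infusion. The endpoints are exploratory and descriptive, with no hypothesis test.

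Most of this stands, and it makes widespread mistiming less likely. It does not remove the conflict: 5.5.5.3 is current operative text, and no rule of precedence is given. Detectability helps only if the analysis uses the recorded times, and the SAP window does not call for that. The SAP's baseline definition would exclude a post-infusion value, but its window and averaging rule would admit one, so a programmer has two rules to choose between.

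**Conclusion.** The inconsistency is real and should be corrected, at low priority. Under 5.5.5.3 as written, an active-arm patient has no valid PD baseline; under footnote 12 the patient does. The number affected is between 0 and 36 of 54, assuming the planned 18 per arm, and cannot be narrowed from the documents.

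A reader might infer more than this supports:

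- **That the PD baseline is lost throughout the active arms.** That is the upper end of the range and requires every site to disregard footnote 12.
- **That the mechanistic comparison is biased in a known way.** The effect of a single infusion on each marker is not given. Under the strict baseline definition the result would be missing values rather than a shift.
- **That efficacy conclusions are at risk.** The primary endpoint does not use these samples. Ferritin, LDH and D-dimers come from the local laboratory schedule (Protocol 5.5.3.7), which samples at screening and Visits 1 to 7 without end-of-infusion timing.

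**What to change.** In the protocol, reconcile 5.5.5.3 with footnote 12:

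- State that the Visit 1 PD sample is pre-dose, in line with the documents' own definition of baseline.
- Confine end-of-infusion timing to visits at which the patient's arm has a scheduled infusion. This leaves out emapalumab at Visit 6, standard of care at every visit, and all arms at Visits 7 to 9.
- Name Visit 7 in footnote 12, since the table already marks a sample there.
- Keep the condition that Visits 8 and 9 are sampled only if the patient attends the clinic, and carry it into 5.5.5.3.

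In the SAP, add to 8.1 or 12.4.3 that the PD baseline must be a sample time-stamped before the start of the first infusion (for standard of care, any Day 1 sample). Post-infusion Day 1 values are to be excluded from baseline and from same-day averaging. Report by arm how many patients lack a PD baseline for this reason.

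The cost is a short wording change in 5.5.5.3 and the footnote, and a sentence or two in the SAP. No additional samples or data items are needed: sampling and infusion times are already recorded, so samples already taken at the wrong time can be identified.

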7.1 Determination of sample size

The study will enroll a total of 54 patients, 18 per arm according to the 1:1:1 randomization.

The sample size has been estimated based on the following assumptions:

- An overall one-sided significance level for efficacy of 0.097 (9.7%) and a power of 74% for each comparison under the assumption that the true success rates are 50% in the SoC group increasing to 80% in the emapalumab or anakinra groups.
- The study will consist of two stages, with equal numbers of patients randomised into Stage 1 and into Stage 2 per treatment arm.
- There is the potential to stop for futility or for efficacy of emapalumab or anakinra (or both) at the end of Stage 1, but only the futility rule is binding and irrespective of the Stage 1 results, the study will not be stopped for efficacy but continue to accrue safety data.

More specifically:

• The emapalumab or anakinra arm (or both) will be stopped at the end of Stage 1 for futility if the one-sided p-value in favour of emapalumab/anakinra is > 0.690.

Confidential

- Efficacy of the emapalumab or anakinra arm (or both) will be declared at the end of Stage 1 if the one-sided p-value in favour of emapalumab/anakinra is < 0.025.
- If the trial continues to Stage 2, efficacy will be declared at the end of Stage 2 if the onesided p-value in favour of emapalumab/anakinra is < 0.159.

The calculations on the operating characteristics of this design have been undertaken using PASS, Version 14: Group-Sequential Tests for Two Proportions (Simulation).

The value for the type I error has been chosen in recognition of the urgent unmet medical need to allow the identification of a signal, at least, from a statistical perspective. Having seen a statistical signal, it is then a matter of evaluating whether the observed treatment differences represent clinically relevant effects that can satisfy that unmet need.

Assuming no untoward safety signal is observed and no futility stopping occurs at the Stage 1 interim, the decision may be taken to increase the sample size beyond 54 patients in order to accrue further safety and efficacy data. Details of this would be described in a protocol amendment.

In case the outcome is statistically convincing, i.e. statistically significant on a 5% level in the stage 2 analysis, efficacy will be considered confirmed and the results may, where warranted, be used to seek regulatory approvals.

7.2 Definition of study populations

All efficacy analyses will be conducted on the modified intention-to-treat (mITT) population which will comprise all randomized patients except patients who did not receive study treatment or patients who tested negative to SARS-CoV-2 diagnosis confirmation by PCR testing.

In case of exclusion due to tested negative to SARS-CoV-2 diagnosis confirmation by PCR testing, additional patients may be recruited to ensure an adequate number of evaluable patients for the efficacy analysis.

The Safety population will comprise all patients who received at least one dose of study treatment or standard of care.

Patients will be included in the groups to which they were randomized for all evaluations of efficacy and in the groups according to treatment received for all evaluations of safety.

7.3 Overall statistical and analytical plan

Statistical analysis will be performed using SAS software Version 9.4 or later (SAS Institute, Inc, Cary, North Carolina, United States).

